### **The aim of the study**

The aim of the study was to determine the effects of SRP supplemented with the local i-PRF application, in comparison with SRP alone, on periodontal disease course.

### **Study population**

This study was a randomized controlled clinical trial with a split- mouth study design. Thirty systemically healthy chronic periodontitis (CP) patients, 13 male and 17 female, age  $38.00 \pm 10.12$  years, range 22 – 64 years were recruited from the Department of Periodontology and Oral Medicine, School of Dental Medicine, University of Belgrade. The study protocol was approved by the Ethics Committee of the School of Dental Medicine, University of Belgrade (36/11) and is in compliance with Helsinki Declaration. After being informed of the research methods, all the participants submitted written consent for the enrolment in the study. The study was registered at ClinicalTrials.gov as “NCT04178590”.

The patients were enrolled in the study according to the following inclusion criteria: adults (age between 20 and 75 years), without systemic and/or other oral disease or ongoing drug therapy, which might have an impact on the clinical signs and symptoms of periodontitis, the presence of minimum 6 teeth per quadrant, at least two teeth with periodontal probing depth (PPD)  $\geq 5\text{mm}$  and minimum clinical attachment level (CAL) 3 mm in each quadrant, and a horizontal bone loss, no involvement of furcation degree II or III of both quadrants of the mandible or maxilla, confirmed by full-mouth radiograph images.

Patients who underwent antibiotic therapy during the last 6 months or had initial and/or surgical periodontal treatment within last 12 months, patients with diabetes or in need of long-term use of anti-inflammatory and immunosuppressive medication, current or former smokers, as well as women who are pregnant or lactating, were excluded from the study.

## **Periodontal examination**

Immediately before the first treatment, as well as at 1, 3 and 6 months, periodontal examinations were carried out by the same examiner. The examination was conducted on all teeth and tooth sites, except the third molars and the tooth sites associated with furcation involvements of II and III degree (Hamp et al. 1975). To identify disease progression, certain variables were recorded from the mesio-buccal, mid-buccal, disto-buccal, disto-lingual, mid-lingual, and mesio-lingual surfaces of each tooth: clinical attachment level (CAL), gingival margin level (GML), periodontal probing depth (PPD), bleeding on probing (BOP), and plaque index (PI). The examiner, a specialist in periodontology, performed and noted down all the recordings. The examiner had previously obtained the adequate level of competence and reproducibility skills according to the various clinical parameters and indices which were going to be utilized (Polson 1997). To avoid blood contamination, GCF collection was conducted one day after clinical examination, after non-surgical periodontal treatment.

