## **Supragingival scaling and root planing and oral hygiene instructions**

At the beginning of the study, the patients were thoroughly instructed on self-performed oral hygiene consisting of: use of the modified Bass brushing technique, a soft manual toothbrush, a regular toothpaste twice a day, and use of inter-dental brushes once a day. A full-mouth SRP was conducted using ultrasonic scaler and hand instruments (Hu-Friedy, Chicago, IL) under local anesthesia in one or two sessions during the period of 24 hours. The standard of oral hygiene was checked at each examination visit and further instructions were provided according to individual requirements. Three months following the completion of the baseline treatment, all the patients were recalled for professional supragingival plaque control and reinforcement of oral hygiene. Additionally, reinstrumentation was conducted by using the ultrasonic device in all the sites with a remaining PPD of  $\geq 5\text{mm}$ .

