## **Preparation of i-PRF**

Blood samples were taken into two 10 ml tubes and prepared for i-PRF preparation. The whole blood without anticoagulant was then centrifuged at 700 rpm for 3 min ( $60\times g$ ) at room temperature

by a Duo Centrifuge (Process for PRF, Nice, France). The upper liquid layer was taken as i-PRF using a syringe. The i-PRF was applied in one quadrant (treatment group) of the chosen jaw (mandibula or maxilla), whereas the physiological saline was inserted in the opposite side (control group). Treatment allocation was decided by a toss of a coin. i-PRF was enabled to hold for a longer time by applying it into periodontal pockets through perforations at the point of interdental space on individually formed occlusal splints. After 15 minutes the splint was removed.

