### **Gingival crevicular fluid (GCF) sampling**

GCF was sampled at baseline and 1-, 3- and 6-month follow-ups, one day after clinical examination from two counter lateral periodontal pockets with PPD  $\geq$  5 mm, either in mandibula or maxilla. GCF was collected by absorbent paper strips (Periopaper, Amityville, NY, USA) after supragingival plaque had been removed, the tooth gently rinsed with water, air-dried and isolated with cotton rolls to avoid contamination from saliva. Four strips were inserted consecutively into the gingival sulcus up to 3 mm leaving them for 30s and pooled in two separate dried microcentrifuge tubes. The absorbed GCF volume was immediately estimated by using a calibrated instrument. Afterwards, the samples were stored at  $-70$  °C pending the analyses.

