### **Protein quantification with ELISA**

Quantification of GCF biomarkers of periodontal disease (MMP -8, TNF-  $\alpha$  and ALP) was performed using enzyme-linked immunosorbent assays (ELISA). GCF samples were defrosted by soaking the paper strips into 150  $\mu$ l of 0,05% Tween 20 solution in sterile Phosphate-buffered saline (PBST) and eluted by 20 minutes of vortexing followed by 10 minutes of centrifugation at 10000  $\times$  g at room temperature. Immediately after centrifugation the supernatant was collected and used to carry out the assays. Protein quantification was performed in duplicate using following ELISA kits: Human Total MMP-8 Quantikine ELISA Kit (R&D Systems, Minneapolis, MN, USA); Human Tumor Necrosis Factor Alpha (TNF- $\alpha$ ) and Human Alkaline Phosphatase (ALP) ELISA kits (Elabscience Biotechnology, Wuhan, China) according to manufacturer's recommendations. Optical density of each well was measured after color development at 450 and 570 nm wavelength using microplate reader (RT 2100C, Rayto Life and Analytical Sciences, Shenzhen, China). Concentrations of tested proteins were determined from generated standard curve.

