### **Quantification of microorganisms**

Bacterial DNA was isolated using a standard salting-out method. DNA extracts were stored at  $-70^{\circ}\text{C}$  prior to quantitative PCR (qPCR) analysis. The amplification of target region for 16S rRNA was performed as previously described (Brajović, Popović, Puletić, Kostić, & Milašin, 2016), using SensiFAST SYBR® Hi-ROX Kit (Bioline Reagents Ltd, London, UK) and the following primers: Fw 5'-TCCTACGGGAGCACAGT'-3' and Rv 5'GGACTACCAGGTATCTAACCTGTT-3'. *Prevotella melaninogenica* (ATCC 25845) was used as reference strain for standard curve analysis, and the results were obtained as total gene copy number.

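### As written, the baseline gingival crevicular fluid sample follows the start of scaling and root planing; its true timing must be established before any biomarker change from untreated disease is claimed

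*Protocol*

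**What the plan says.** Four protocol sections and the SAP bear on the order of events.

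- Periodontal examination, on the clinical visits: "Immediately before the first treatment, as well as at 1, 3 and 6 months, periodontal examinations were carried out by the same examiner".
- Periodontal examination, on the fluid samples: "To avoid blood contamination, GCF collection was conducted one day after clinical examination, after non-surgical periodontal treatment".
- Gingival crevicular fluid (GCF) sampling, which names baseline together with the follow-ups: "GCF was sampled at baseline and 1-, 3- and 6-month follow-ups, one day after clinical examination".
- Supragingival scaling and root planing and oral hygiene instructions: full-mouth SRP was done "under local anesthesia in one or two sessions during the period of 24 hours".
- Preparation of i-PRF: i-PRF went to one side and saline to the other. No time is given relative to the baseline GCF sample.

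The samples supply three markers, MMP-8, TNF-alpha and ALP (Protein quantification with ELISA). The SAP tests every measurement across visits within each side, and compares the two sides by a paired test at baseline and at each follow-up. It also plans linear regression for CAL at 6 months and logistic regression for the difference between groups, without listing the predictors.

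**The concern.** A baseline value is normally understood as the state before treatment. Here the clinical measures have such a baseline, because the examination comes before treatment. The biomarkers, as the protocol is worded, do not. One visit label would then cover two different points in the course of treatment.

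Two inferences are at stake. First, a within-side statement that a biomarker rose or fell from baseline would compare later samples with one taken about a day after instrumentation began, and would not describe change from untreated disease. Second, if i-PRF or saline had also been applied by then, the between-side biomarker test at baseline would not check pre-treatment balance, because the two sides would already have been treated differently.

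**Working it through.** The plan states no figure on this point. The check is a timeline, followed by a count of the tests that use the sample.

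**Timeline as written** (baseline examination set at hour 0; the unnamed first treatment taken to be SRP):

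| Event | Time | Source |
|---|---|---|
| Baseline examination | hour 0, immediately before treatment | Periodontal examination |
| Full-mouth SRP | starts just after hour 0, spans up to about 24 h | Supragingival scaling and root planing |
| GCF sample labelled baseline | about hour 24 | GCF sampling; Periodontal examination |
| i-PRF or saline | not stated relative to GCF | Preparation of i-PRF |

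Two routes lead to the same order. The closing clause of "To avoid blood contamination, GCF collection was conducted one day after clinical examination, after non-surgical periodontal treatment" says it outright. Without that clause, an examination immediately before treatment plus a one-day lag still puts the sample after SRP began. Whether SRP was complete by then is less clear, because a second session could fall near hour 24.

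**The alternative order** is examination, GCF the next day, then SRP. It needs *immediately* to allow a gap of a day or more, and it needs the closing clause of the GCF sentence to be wrong or to refer to follow-up samples only. Either way the Periodontal examination section needs correcting or clarifying.

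**Which analyses use the sample.** Inputs: 30 patients (Study population), 4 visits, 3 biomarkers, 2 sides. Assumptions: one pocket per side and complete sampling.

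- Side-samples: 30 × 2 × 4 = 240, of which 30 × 2 = 60 are labelled baseline.
- Within-side overall tests: 3 × 2 = 6. All 6 include the baseline visit.
- Within-side visit contrasts: the SAP lists none, so the share depends on which set is assumed, each multiplied by 6 (biomarker by side):

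| Assumed contrasts | Per biomarker and side | With baseline | Total affected |
|---|---|---|---|
| All pairs of visits | 4 × 3 / 2 = 6 | 3 | 18 of 36 (50%) |
| Each follow-up against baseline | 3 | 3 | 18 of 18 (100%) |
| Consecutive visits | 3 | 1 | 6 of 18 (33%) |

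- Between-side biomarker tests: 3 × 4 = 12. Three are at baseline; 12 − 3 = 9 are at follow-up and do not use the sample.
- Direct CAL comparisons: none uses the sample.
- Regression models: unknown, because baseline biomarkers are neither listed as predictors nor excluded.

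These counts show how often the sample enters the analysis. They do not show how far any result would move.

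**The case against.** The strongest reply is that the literal order does not fit the protocol's own reason for the lag. If the aim was to keep blood out of the strips, a day's gap after probing makes sense, while sampling a day after full-mouth instrumentation makes less. The GCF section also ties the sample to the examination and not to treatment, and calls it baseline. The clause about non-surgical treatment may have been meant for the follow-up samples.

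This stands as to what actually happened. A reader might infer that the samples were in fact taken too late; the documents do not support that. They show text in conflict with itself, and only the records can settle the timing. The reply does not remove the point, because even the benign order requires the protocol wording to be corrected.

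It can also be said that the matter is secondary. The study aim is a comparison between sides, CAL is the only outcome named as primary, and the documents nowhere promise an estimate of biomarker change from untreated disease. This too is fair and limits the reach. However, the SAP does plan within-side tests over time for all measurements, and a reader would ordinarily take a contrast with baseline as change from the untreated state.

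**Conclusion.** The concern holds in limited form and should be fixed. As written, the baseline GCF sample follows the start of SRP, and no pre-treatment GCF sample is described; the actual timing is not established. The consequences are conditional. If the sample followed the start of SRP, within-side biomarker contrasts with that visit are not change from untreated disease: all 6 overall tests, and between 33% and 100% of visit contrasts depending on the set used. If i-PRF or saline also came first, the 3 between-side biomarker tests at baseline are not checks of pre-treatment balance.

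A reader might go further and infer that the trial's main comparison is compromised. The documents do not support that: the direct between-side comparisons of CAL, and of the biomarkers at 1, 3 and 6 months, do not use this sample. Nor is it safe to say that no CAL analysis uses it, since the regression predictors are not listed. No size or direction of bias can be computed. Confidence is medium: the conflict in the text is firm, the true order of events is not known.

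**What to change.** 1. Check the recorded times of the baseline GCF sample, SRP and the i-PRF or saline application. Reconcile the protocol sections on examination, SRP, i-PRF preparation and GCF sampling, and state the order explicitly.
2. If GCF came before SRP, correct the Periodontal examination section and keep the SAP tests as they are.
3. If GCF came after SRP had started, or the order cannot be shown:
   - Label the sample only by what is known: *1 day after baseline examination*, adding *after SRP* only if the records show it.
   - Make no claim of change from a pre-treatment biomarker level.
   - Do not enter the sample as a pre-treatment biomarker value in any regression.
   - Rest biomarker conclusions on the paired between-side comparisons at 1, 3 and 6 months.

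The cost is a record check and wording changes in the protocol and SAP. No new samples or different tests are needed. The downside falls in case 3: no change from a pre-treatment biomarker level can then be reported.

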## **Supragingival scaling and root planing and oral hygiene instructions**

At the beginning of the study, the patients were thoroughly instructed on self-performed oral hygiene consisting of: use of the modified Bass brushing technique, a soft manual toothbrush, a regular toothpaste twice a day, and use of inter-dental brushes once a day. A full-mouth SRP was conducted using ultrasonic scaler and hand instruments (Hu-Friedy, Chicago, IL) under local anesthesia in one or two sessions during the period of 24 hours. The standard of oral hygiene was checked at each examination visit and further instructions were provided according to individual requirements. Three months following the completion of the baseline treatment, all the patients were recalled for professional supragingival plaque control and reinforcement of oral hygiene. Additionally, reinstrumentation was conducted by using the ultrasonic device in all the sites with a remaining PPD of  $\geq 5\text{mm}$ .

## **Preparation of i-PRF**

Blood samples were taken into two 10 ml tubes and prepared for i-PRF preparation. The whole blood without anticoagulant was then centrifuged at 700 rpm for 3 min ( $60\times g$ ) at room temperature

by a Duo Centrifuge (Process for PRF, Nice, France). The upper liquid layer was taken as i-PRF using a syringe. The i-PRF was applied in one quadrant (treatment group) of the chosen jaw (mandibula or maxilla), whereas the physiological saline was inserted in the opposite side (control group). Treatment allocation was decided by a toss of a coin. i-PRF was enabled to hold for a longer time by applying it into periodontal pockets through perforations at the point of interdental space on individually formed occlusal splints. After 15 minutes the splint was removed.

### **Gingival crevicular fluid (GCF) sampling**

GCF was sampled at baseline and 1-, 3- and 6-month follow-ups, one day after clinical examination from two counter lateral periodontal pockets with PPD  $\geq$  5 mm, either in mandibula or maxilla. GCF was collected by absorbent paper strips (Periopaper, Amityville, NY, USA) after supragingival plaque had been removed, the tooth gently rinsed with water, air-dried and isolated with cotton rolls to avoid contamination from saliva. Four strips were inserted consecutively into the gingival sulcus up to 3 mm leaving them for 30s and pooled in two separate dried microcentrifuge tubes. The absorbed GCF volume was immediately estimated by using a calibrated instrument. Afterwards, the samples were stored at  $-70$  °C pending the analyses.

### **Protein quantification with ELISA**

Quantification of GCF biomarkers of periodontal disease (MMP -8, TNF-  $\alpha$  and ALP) was performed using enzyme-linked immunosorbent assays (ELISA). GCF samples were defrosted by soaking the paper strips into 150  $\mu$ l of 0,05% Tween 20 solution in sterile Phosphate-buffered saline (PBST) and eluted by 20 minutes of vortexing followed by 10 minutes of centrifugation at 10000  $\times$  g at room temperature. Immediately after centrifugation the supernatant was collected and used to carry out the assays. Protein quantification was performed in duplicate using following ELISA kits: Human Total MMP-8 Quantikine ELISA Kit (R&D Systems, Minneapolis, MN, USA); Human Tumor Necrosis Factor Alpha (TNF- $\alpha$ ) and Human Alkaline Phosphatase (ALP) ELISA kits (Elabscience Biotechnology, Wuhan, China) according to manufacturer's recommendations. Optical density of each well was measured after color development at 450 and 570 nm wavelength using microplate reader (RT 2100C, Rayto Life and Analytical Sciences, Shenzhen, China). Concentrations of tested proteins were determined from generated standard curve.

### **Quantification of microorganisms**

Bacterial DNA was isolated using a standard salting-out method. DNA extracts were stored at  $-70^{\circ}\text{C}$  prior to quantitative PCR (qPCR) analysis. The amplification of target region for 16S rRNA was performed as previously described (Brajović, Popović, Puletić, Kostić, & Milašin, 2016), using SensiFAST SYBR® Hi-ROX Kit (Bioline Reagents Ltd, London, UK) and the following primers: Fw 5'-TCCTACGGGAGCACAGT'-3' and Rv 5'GGACTACCAGGTATCTAACCTGTT-3'. *Prevotella melaninogenica* (ATCC 25845) was used as reference strain for standard curve analysis, and the results were obtained as total gene copy number.

Effect of Injectable Platelet-Rich Fibrin (i-PRF) in Initial Treatment of Chronic Periodontitis

- **NCT04178590**
- **26 April, 2020**

Statistical analysis

Statistical Package for Social Science (SPSS software package, version 26.0; SPSS Inc., Chicago, IL, USA) was used for all the data analyses. For numerical data, mean values, medians, standard deviations (SD) and ranges were used for description. The distributions of all outcome values were examined using the Kolmogorov–Smirnov normality test and depending on the distribution, measurements at baseline and at each follow-up between two treatment groups were compared using paired Student's t-test or Wilcoxon signed-rank test. Comparisons within each treatment group for all the measurements were done by repeated measures ANOVA with Bonferroni correction or Friedman and Wilcoxon signed-rank test. Univariate and multivariate logistic regression models were used to assess the predictors of difference between treatment groups. Univariate and multivariate linear regression models were for the predictors of primary outcome (CAL) at 6 months. The differences were considered as significant when the p value was <0.05 . Study power was calculated using DSS Research, for primary outcome (CAL) at 6 months and it was above 90%.

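### The specified treatment comparison of 6-month CAL leaves out baseline CAL; adjusting for it could cheaply tighten the primary estimate, although the planned test is not biased

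*SAP*

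**What the plan says.** The SAP (Statistical analysis) says that "measurements at baseline and at each follow-up between two treatment groups were compared using paired" t-tests or Wilcoxon signed-rank tests, depending on the distribution. It names no change score and no baseline covariate. The repeated-measures ANOVA and Friedman tests are run within each treatment group, so they do not compare treatments.

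Two sets of regression models are also planned:
- "Univariate and multivariate linear regression models were for the predictors of primary outcome (CAL) at 6 months"
- "Univariate and multivariate logistic regression models were used to assess the predictors of difference between treatment groups"

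Neither lists covariates, and neither is presented as the treatment comparison. An adjusted treatment estimate is therefore neither planned nor excluded.

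The SAP says power was calculated "for primary outcome (CAL) at 6 months and it was above 90"%, without giving an effect, an SD or the sidedness of the test.

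The Protocol supplies what adjustment would need. Under Periodontal examination: "Immediately before the first treatment, as well as at 1, 3 and 6 months, periodontal examinations were carried out by the same examiner". CAL is among the variables for which "certain variables were recorded from the mesio-buccal, mid-buccal, disto-buccal, disto-lingual, mid-lingual, and mesio-lingual surfaces of each tooth". Under Preparation of i-PRF: "Treatment allocation was decided by a toss of a coin".

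**The concern.** Pairing removes what the two sides of one mouth have in common. It does not remove a difference between the sides that existed before treatment. A coin toss makes such differences random in direction, so they do not bias the comparison on average. Any part of them that persists to 6 months is still carried as noise in the 6-month side difference. Testing the baseline values separately, as the SAP does, brings none of that information into the 6-month estimate.

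What is at stake is the width of the confidence interval for the primary effect, which may be wider than the collected data allow. How far baseline differences persist is unknown. The 3-month visit could weaken the link: "Additionally, reinstrumentation was conducted by using the ultrasonic device in all the sites with a remaining PPD of" 5 mm or more.

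**Working it through.** **Inputs from the documents.** 30 patients and a split-mouth design (Protocol, Study population); significance at p < 0.05 and stated power above 90% (SAP).

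**Assumptions.** Two-sided test; one CAL value per side per patient; no dropout; expected baseline side difference of zero (coin toss); r between baseline and 6-month side differences varied from 0 to 0.7.

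**1. The plan's own figure.** Power above 90% cannot be reproduced, because no effect or SD is given. It can be inverted. For a paired t-test with n = 30, df = 29 and noncentrality d√30, 90% power needs d = 0.612 SD of the side difference. The normal approximation gives (1.960 + 1.282)/√30 = 0.592. This d anchors the power figures below.

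**2. Variance after adjustment.** Regress the 6-month side difference on the baseline side difference and take the intercept as the treatment effect. Its variance, in units of the residual-free SD², is (1 − r²)(1/n + x̄²/Sxx), where x is the baseline difference. Averaged over x and divided by the unadjusted 1/n:

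ratio = (1 − r²)(1 + 1/(n − 3)) = (1 − r²)(28/27)

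The CI-width ratio is about the square root of this, times t(28)/t(29) = 2.048/2.045. Adjusted power uses the noncentral t with df = 28, averaged over the distribution of x.

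| r | Variance ratio | 95% CI width ratio | Adjusted power (unadjusted 90%) | Equivalent pairs, 30/ratio |
|---|---|---|---|---|
| 0 | 1.037 | 1.02 | 88.9% | 28.9 |
| 0.3 | 0.91 × 28/27 = 0.944 | 0.97 | 91.5% | 31.8 |
| 0.5 | 0.75 × 28/27 = 0.778 | 0.88 | 95.6% | 38.6 |
| 0.7 | 0.51 × 28/27 = 0.529 | 0.73 | 99.3% | 56.7 |

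**3. Break-even.** The ratio equals 1 when r² = 1 − 27/28 = 1/28, so r = 0.189. On power at 0.612 SD, which also counts the lost degree of freedom, break-even is r = 0.197.

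**4. The Wilcoxon branch.** Simulated power at the same effect, 60,000 trials per cell:

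| Distribution of differences | Test | r = 0 | 0.3 | 0.5 | 0.7 |
|---|---|---|---|---|---|
| Normal | Wilcoxon | 88.6% | 88.6% | 88.5% | 88.6% |
| Normal | Adjusted | 88.8% | 91.2% | 95.6% | 99.3% |
| t, 4 df, scaled to SD 1 | Wilcoxon | 95.3% | 94.5% | 94.2% | 93.5% |
| t, 4 df, scaled to SD 1 | Adjusted | 89.1% | 91.2% | 94.6% | 98.2% |

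With heavy tails the regression overtakes Wilcoxon only near r = 0.5.

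**5. Validity.** Type I error was 4.5 to 5.2% for the paired t, Wilcoxon and adjusted tests under both distributions (20,000 trials per cell). In separate runs with normal differences, the unadjusted mean and the adjusted intercept were both centred on the true effect.

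**6. A change score is not a substitute.** With equal variances at the two visits its variance ratio is 2(1 − r): 2.0 at r = 0, 1.4 at 0.3 and 1.0 at 0.5. It is less precise than the planned comparison whenever r < 0.5.

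**The case against.** The strongest reply is that nothing in the plan is wrong. A paired test in a randomised split-mouth trial is valid, and the choice between two valid estimators is optional. That stands: this is an efficiency point, not an error.

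Further points, and what remains of them:
- **r is unknown.** No section places r at 0.5 or above. Pairing already removes between-patient variation, and the entry rule of at least two qualifying teeth in each quadrant may limit baseline asymmetry. This stands, and it is why the result is given as a range.
- **Exactly 90% is the floor of what the SAP claims.** If unadjusted power is 95%, adjusted power is 94.2%, 95.9% and 98.3% at r = 0, 0.3 and 0.5, so the power gain shrinks. The variance and CI-width ratios do not change.
- **Least squares can lose to Wilcoxon.** This stands for heavy-tailed differences. The loss is about 6 points at r = 0 (95.3% against 89.1%), and keeping Wilcoxon as a sensitivity analysis does not restore the power of the main test.
- **The planned linear regression might already include baseline CAL and treatment.** It might, but the SAP does not say so.
- **Unit of analysis.** The SAP does not say how six surfaces per tooth become an analysed value. If sites were analysed individually, these figures would not apply and clustering would be the larger problem.
- **Timing.** The SAP is in the past tense, so a change to the primary analysis may no longer be open.

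**Conclusion.** The concern holds as a modest point about precision. The SAP's only specified treatment comparison of 6-month CAL ignores baseline values that were collected on both sides. Adjustment would reduce the variance of the effect estimate by about 6% at r = 0.3, 22% at 0.5 and 47% at 0.7, and would increase it by about 4% at r = 0. The gain is small at r = 0.3 and material from about 0.5. It corrects no bias, and the planned test keeps its 5% error rate.

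These figures rest on 30 complete pairs with one CAL value per side, two-sided 0.05, and an assumed r; the power figures are also tied to an unadjusted power of exactly 90%. Normality matters as well: with heavy-tailed differences the advantage over Wilcoxon appears only near r = 0.5. Confidence is medium because r cannot be known from the documents.

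**What to change.** Define one mean CAL per side per patient at each visit. Regress the within-patient 6-month CAL difference (i-PRF minus control) on the within-patient baseline CAL difference, and report the intercept with its 95% CI as the treatment effect. Keep the planned paired t or Wilcoxon test as a sensitivity analysis.

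If outcomes have already been seen, leave the paired test as planned and report the adjusted estimate beside it, labelled post hoc.

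Cost: no new data, one degree of freedom, and 1 to 2 power points if r is near 0. With heavy-tailed differences the regression can fall about 6 points below Wilcoxon at r = 0, which is why the planned test should still be reported.

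### The between-side tests make no stated use of baseline, no comparison of change between sides is planned, and the within-side tests over time carry no information about i-PRF

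*SAP*

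**What the plan says.** The protocol's aim is comparative and longitudinal: to "determine the effects of SRP supplemented with the local i-PRF application, in comparison with SRP alone, on periodontal disease course". Under Study population it states: "This study was a randomized controlled clinical trial with a split- mouth study design". There are 30 patients, so 30 pairs of sides. Under Preparation of i-PRF: "Treatment allocation was decided by a toss of a coin". Clinical examinations take place before treatment and at 1, 3 and 6 months.

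The SAP plans two sets of tests that matter here:

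- Between sides: "measurements at baseline and at each follow-up between two treatment groups were compared", by paired t-test or Wilcoxon signed-rank test.
- Over time: "Comparisons within each treatment group for all the measurements were done by repeated measures ANOVA" with Bonferroni correction, or by Friedman and Wilcoxon tests.

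It also mentions logistic regression for predictors of a difference between groups and linear regression for predictors of 6-month CAL. Neither lists its predictors, and neither names a time term. CAL at 6 months is the primary outcome, but the SAP does not say which analysis decides whether i-PRF worked.

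**The concern.** The aim concerns the course of disease under i-PRF against control. The analyses that follow the course are run inside each side. The analyses that compare sides look at one visit at a time, with no stated use of the baseline value. The two sets are not joined by a difference in change, a baseline-adjusted contrast or a side-by-visit term.

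Two things are at stake. The first is precision: a baseline measurement is taken on each side and then left out of the comparison it could sharpen. The second is interpretation. Both sides receive full-mouth SRP, hygiene instruction and, at 3 months, reinstrumentation of sites with PPD still at 5 mm or more. A within-side p value mixes all of this with any i-PRF effect. A significant change on one side and a non-significant change on the other does not show that the sides differ, and the SAP does not mark these tests as descriptive.

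**Working it through.** **1. The plan's own figure.** The SAP gives power above 90% for 6-month CAL, without a difference, SD, correlation or named test, so it cannot be reproduced. For a paired t-test with 30 pairs and two-sided alpha 0.05 (sidedness assumed), 90% power needs a standardised paired difference of (1.960 + 1.282)/√30 = 0.59 by normal approximation, or 0.61 by the noncentral t. Nothing in the documents allows a check of that value.

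**2. How often a one-sided pattern arises by chance.** Assume 30 pairs and the same true change on both sides (no i-PRF effect). Let dz be the within-side mean change divided by its SD, and rho the correlation between the two sides' changes. The documents give neither, so both are assumed over a range. Count trials in which the i-PRF side is significant and the saline side is not (40,000 simulated trials per setting).

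| dz | alpha | within-side power | rho 0.3 | rho 0.5 | rho 0.7 |
|---|---|---|---|---|---|
| 0.37 | 0.05 | 0.50 | 0.20 | 0.17 | 0.13 |
| 0.50 | 0.05/6 | 0.47 to 0.48 | 0.21 | 0.17 | 0.13 |
| 0.60 | 0.05 | 0.89 | 0.09 | 0.07 | 0.06 |
| 0.80 | 0.05 | 0.99 | 0.01 | 0.01 | 0.01 |
| 1.00 | 0.05 | 1.00 | 0.00 | 0.00 | 0.00 |

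The divisor 6 is the number of pairs among four visits (4 × 3/2). Hand check at rho 0: the rate is power × (1 − power), or 0.5 × 0.5 = 0.25 at its maximum, and simulation gives 0.25. So 50% power is the peak of the curve.

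A direct paired test of the two changes wrongly favours i-PRF in 2.5% of trials. In the first two rows, only 10% to 13% of the i-PRF-only patterns show a difference between sides at p<0.05.

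**3. What baseline adjustment gains.** Assume a true side difference of 0.4 SD and between-side correlation 0.5. The SD of the side difference is √(2(1 − 0.5)) = 1, so the standardised paired difference is 0.4 and the planned test has about 56% power. Adjusting for the baseline side difference, with correlation r to follow-up, multiplies the residual SD by √(1 − r²):

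- r = 0.5: 0.4/0.866 = 0.46, power about 67%.
- r = 0.7: 0.4/0.714 = 0.56, power about 83%.

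Both power values include the cost of estimating the slope. An unadjusted change score is less dependable, because its SD is multiplied by √(2(1 − r)): 1.18 at r = 0.3, 1.00 at r = 0.5, 0.77 at r = 0.7. It loses precision when r is below 0.5.

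**4. Why the random effects must be specified.** With six post-baseline values per patient (2 sides × 3 visits), a model with only a patient effect treats visits on the same side as independent once patient is removed. Take patient-by-side variance 0.5 and residual variance 0.2 (assumed). The pooled residual is [29 × (3 × 0.5 + 0.2) + 116 × 0.2]/145 = 0.50. For the visit-averaged side effect, the model uses 2 × 0.50/3 = 0.33 where the true value is 2 × (0.5 + 0.2/3) = 1.13. The SE is too small by a factor √(0.33/1.13) = 0.54, which gives a false-positive rate of about 28%. Over patient-by-side variances of 0.1 to 0.5 and residual variances of 0.2 to 0.5, the rate is 10% to 28% for the visit average and 6% to 10% at 6 months.

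**The case against.** A reader might infer that the SAP never compares the two courses and that the study question has no direct test. The documents do not support that. The sentence before the within-side tests plans paired comparisons between sides at every follow-up. With coin-toss allocation, each is a valid test of i-PRF at that visit, and the three together describe the treatment difference over time. This objection stands in full: the primary question is tested directly.

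A reader might also infer that a significant result on one side only will be reported as an i-PRF effect. Neither document says so. The rates in step 2 belong to a decision rule that the plan does not state, and the 13% to 20% is at or near the peak for those correlations. Both sides are treated with SRP, so CAL and PPD may change strongly from baseline, and the pattern would then be rare. The exposure is greater for weaker contrasts, such as 1 to 3 months, 3 to 6 months, or biomarkers with small changes.

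Regression to the mean should not be pressed either. Clinical measurements cover all teeth and nearly all sites, and selection of measured sites by depth is explicit only for the GCF pockets.

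What remains is that baseline has no stated use between sides, change is not compared between sides, and the role of the within-side tests is left open.

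**Conclusion.** The point holds as a gap in efficiency and clarity, not as a missing or invalid primary test. The paired 6-month CAL comparison is sound. The within-side tests cannot support a statement about i-PRF, and the SAP should say so. If they were used that way, the chance rate would be 13% to 20% at about 50% within-side power, 6% to 9% at 89%, about 1% at 99%, and practically nil when both sides improve strongly. All these rates assume normal changes, equal true change on both sides and correlation 0.3 to 0.7; at correlation zero the peak is 25%. The gain from baseline adjustment (56% to 67% or 83%) also rests on assumed values, but adjustment uses data already collected.

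**What to change.** - **Decisive test.** Name the 6-month between-side CAL contrast as the test that decides.
- **Adjustment.** At each follow-up, regress the within-patient side difference (i-PRF minus saline) on the baseline side difference, and take the intercept as the effect. Keep the baseline difference centred on zero, its expected value under the coin toss. Centring on the sample mean returns the unadjusted mean difference with an SE too small by √(1 − r²); by normal approximation its null rejection rate is about 9% at r = 0.5 (1.96 × 0.866 = 1.70) and 16% at r = 0.7 (1.96 × 0.714 = 1.40).
- **Or one mixed model.** Include side, visit, side-by-visit and baseline, with patient and patient-by-side random effects or an unstructured within-patient covariance. A patient effect alone is not enough (step 4).
- **Course.** Report the side difference at 1, 3 and 6 months as the answer. Treat the side-by-visit test as supplementary, because a constant benefit from month 1 gives a null interaction.
- **Non-normal outcomes.** Keep the paired Wilcoxon test, or transform.
- **Within-side tests.** Label them descriptive of healing after SRP.
- **GCF baseline.** Clarify when it was sampled before using it as a covariate. The Periodontal examination section places GCF collection after non-surgical treatment, while the GCF sampling section lists a baseline sample.

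The cost is some SAP wording, slightly more analysis, one degree of freedom in the regression, and within-side p values that no longer play any part in inference about i-PRF. No new data are needed.
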